NCT02403817 Training Attention and Eye Movement in ASD 8/8/2019

Study Protocol and Statistical Plan

Current therapies for Autism Spectrum Disorder (ASD) target social and language behaviors, but due to the highlevel nature of these skills any improvement rarely extends beyond the targeted behavior. This project uses new technology to implement a novel concept for behavioral intervention to improve basic attention and eye movement skills in ASD. Children will play gaze-driven video games at home during the intervention, receive pre- and post-training assessment of attention, and eye movement function. Because these basic skills form the foundation for good social communication, training these abilities has the potential to improve a broad spectrum of clinical symptoms, and in young children may affect the course of development.

This is a pilot project with a small clinical trial. The aims are:

1: Conduct video game training system with 2 groups of 20 ASD children/teens/young adults (aged 9-26).

2: Evaluate efficacy of training using 3 levels of outcome measures for pre- and post- testing and followup. Level 1 will be a direct test of attention and eye movement. Level 2 will test attention and eye movement function in a digital environment. Level 3 will test the effect of training on social skills measured by questionnaires and in a live social interaction.

Research Design and Methods

We will recruit 40 male and female children with ASD (ages 9-26) to participate in the clinical trial. Participants will meet the criteria for Inclusion and Exclusion described below (we have an existing pool of potential participants that meet inclusion criteria, but expect to screen 50 children to find 40 that meet study criteria).

Collaborator [name] (Rady Children's Hospital) will be responsible for diagnosis of participants who do not already have required diagnostic assessment. [name] is the Clinical Director Rady Children's Hospital Autism Discovery Institute (ADI). [name] is ADI-R and ADOS reliable and is a certified trainer for both instruments. ASD participants will be recruited by [name] through ADI. We also have a large pool of children and teens with ASD from previous studies who meet diagnostic standards, the majority of whom will be willing to participate in the proposed project.

General inclusion/Exclusion criteria:

- 1. All participants must be cooperative and able to follow instructions.

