- 2. All participants must have normal hearing acuity and corrected-to-normal vision.

Inclusion criteria: All ASD participants will meet diagnostic criteria from the Diagnostic and Statistical Manual of Mental Disorders-IV (DSM-IV), the Autism Diagnostic Interview-R (ADI-R), and the Autism Diagnostic Observation Schedule (ADOS). Nonverbal IQ must be 85 or greater, verbal IQ must be 70 or greater.

Exclusion criteria: ASD participants will be excluded if they have major medical or neurological problems including seizures, diagnosed epileptiform EEG abnormalities, migraine, tuberous sclerosis, fragile *X*, static encephalopathies resulting from prior CNS insults, significant premature birth, and history of exposure to teratogens, metabolic abnormalities, and history of head trauma, cerebral palsy, stroke, meningitis, brain tumor or additional psychiatric diagnoses. Children who are currently participating in vision therapy will be excluded. We will not exclude participation based on use of psychotropic medication.

All participants and parents/caregivers for children will give informed consent. ASD participants who do not have existing ADOS and ADI-R will receive the diagnostic assessment listed above. Diagnostic testing will take place at the Research on Autism and Developing Laboratory, and will be conducted by [name] or by a clinician under her direct supervision. The ADOS will be administered to potential ASD participants in a private testing office, and will take approximately 1 hour; concurrently, the potential participant's parent will fill out the ADI-R in a quiet waiting area. All participants will be paid for their participation in the study.

If individuals are unwilling or unable to complete in-lab testing, we will recruit new participants to complete those experiments. Based on our previous experience with similar clinical groups, we would expect no more than 10-15% of the clinical participants will fail to complete all in-lab testing. If more than two of the participants in the 8-

week study fail to complete more than four weeks of training, we will attempt to improve the user experience based on participant feedback and then recruit new participants to complete that study.

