Gender and Minority Inclusion: Any participant who meets study criteria and agrees to participate will be included. We will not exclude participants based on ethnicity, but because we do not have standardized translations of the standardized testing instruments, we will restrict inclusion to children for whom English is the primary language. The ratio of males to females with ASD in California is 4.6:1, and we expect that our sample will reflect this ratio.

Participation of Children: Interventions to target attention and eye movement problems in ASD (our long-range goal from this feasibility study) are likely to be more effective in children than adults. The goal of this study is to test whether our portable eye-tracking system is easy and durable for children's use at home, and whether the video games are interesting enough to motivate children's compliance for almost daily use over an extended period. This research falls under section 404 of 45CFR 46 Subpart D ("Research not involving greater than minimal risk").

There are 3 phases of study participation: an initial assessment/orientation, an 8-week intervention training phase, and a final evaluation phase.

Assessment/Orientation Phase: Each participant will come to our lab for two sessions that will take place on separate days. Session 1 will include consent and overall instructions, IQ testing (WASI) ⁹, SRS ¹⁰, and baseline measures of attention and eye movement (Spatial Attention Task, Gap-Overlap and Anti-Saccade Eye Movement Tasks). Session 2 will establish baseline measures on the Simulation Task and Social Interaction Task, and will cover the introduction and trial use of the Training System and instructions for home use. Following this initial assessment, scores on the Spatial Attention and Eye Movement tasks will be used to assign children to one of two intervention groups so that the mean and range of those scores are equivalent between groups. During the intervention phase, Group 1 will receive the gaze-contingent training principles game. Group 2 will play the same game as Group 1 in daily training, except that instead of using gaze, the game play will be joystick-driven.

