Intervention Phase: During this 8-week period, study participants will be asked to play a video game at home for a minimum of 30 minutes per day, 5 times per week. Parents/caregivers will oversee the daily in-home training and will be briefed along with the subjects at Session 2. Participants (and parents) will be phoned during the first 3 days of in-home testing to assure that there are no problems with equipment or use of equipment. Participants will return to our lab at 4 weeks, for an abbreviated round of tests (Level 1, to assess attention and eye movement, described below). Game play will be monitored as in our pilot testing using a secure 'dropbox' through which we will receive daily summaries of the amount of time each child has played the games, amount of time spent in calibration, and notes from the child regarding any problems or comments they might have about the games. If we find that a child is not playing the required amount of time, or has excessive calibration time, we will contact the family and follow-up with a home visit to assess the problem if necessary. This system worked very well for us in the pilot testing. Children who withdraw (or whose participation is terminated for failure to play the games) from the study will be replaced. An investigator from the project will always be available to troubleshoot any hardware/software problems, and discuss the child's progress by phone, e-mail, or in-home visits as required.

Final Evaluation Phase At the 8 week lab visit (the end of the intervention period), we will collect postintervention assessment at three outcome levels (direct testing of attention and eye movement and social questionnaires; simulation task testing; real social interaction-- all described below). We will ask trainees and their parents to complete a questionnaire evaluating their experience with particular focus on the ease of use of the equipment and game and the enjoyability of the training game.

Attention/Eye Movement Tests: The following tasks are a direct test of improvement of spatial attention disengagement and orienting and eye movement accuracy and initiation speed.

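### Assignment to gaze or joystick training follows known Level 1 scores with no random or concealed step described, so the between-group tests, mainly at Levels 2 and 3, are exposed to selection bias

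*Combined protocol and SAP*

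**What the plan says.** The only allocation rule is in the Assessment/Orientation Phase of the combined protocol and SAP. After two baseline sessions, "Following this initial assessment, scores on the Spatial Attention and Eye Movement tasks will be used to assign children" to one of two groups "so that the mean and range of those scores are equivalent between groups". Group 1 plays by gaze and Group 2 plays the same games by joystick.

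The Simulation, Social Interaction, SRS and IQ baselines are collected before assignment but are not among the scores named in the rule. Nor is age, which runs from 9 to 26, or medication: "We will not exclude participation based on use of psychotropic medication".

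Replacement is mentioned twice. If too many participants fall short of the training, the team will improve the user experience and "then recruit new participants to complete that study". Under Intervention Phase, children who withdraw or are terminated for not playing "from the study will be replaced". Neither place says which group a replacement joins.

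On purpose, the introduction says "This is a pilot project with a small clinical trial", and the section on participation of children gives a feasibility goal: "The goal of this study is to test whether our portable eye-tracking system is easy and durable". Aim 2, however, is to "Evaluate efficacy of training using 3 levels of outcome measures for pre- and post- testing and followup". The Statistical Plan tests group differences at all three levels, with a MANOVA across groups at Level 1.

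**The concern.** The joystick group is there to separate the effect of gaze control from game play, elapsed time and retesting. It does so only if assignment is unrelated to whatever predicts a child's change.

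Mean and range are properties of a group and do not determine where a given child goes. Whoever assigns must know the scores and the emerging make-up of the groups. By then, staff have also watched the child try the training system in Session 2. A judgement about who would cope with gaze control, or whose family would keep up the schedule, could enter the choice without breaking the rule.

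Age is a plausible route. The section on participation of children expects such interventions to work better in children than in adults, yet age is not balanced and no covariate is named for the group tests.

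At stake is the plan's only between-group evidence on efficacy.

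**Working it through.** The plan gives no alpha, SD, effect size or power figure, so there is no stated number to reproduce. The check has three parts.

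**1. Is there a random or concealed step anywhere?** I found none. The document does not say who assigns, by what procedure, or whether children are assigned in batches or singly. The word for random selection appears once, for target position in the Gap-Overlap Saccade Task.

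**2. How much freedom does the rule leave?**
- From the documents: 40 children, 20 per group, and five Level 1 outcome measures (Statistical Plan, Level 1).
- Assumed: all 40 assigned together; the five measures are the matched scores; scores normal with equal correlation 0-0.5; the tolerances below.
- Possible splits: C(40,20) = 1.378 × 10^11.

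| Requirement on all five scores | Share of splits | Number of splits |
|---|---|---|
| Means within 0.2 SD | 2.2%-4.4% | 3-6 billion |
| Also ranges within 1 SD | 0.3%-0.5% | 0.4-0.7 billion |
| Also ranges within 0.5 SD | about 0.01%-0.03% | 14-41 million |

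The number is share × 1.378 × 10^11; for example, 0.0001 × 1.378 × 10^11 = 13.8 million. The shares are simulation estimates. At a correlation of 0.5 a repeat run gave somewhat more room, up to 0.7% and 0.05% in the last two rows.

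Of the splits that pass on means and on ranges within 1 SD, about 10%-12% differ by more than 0.5 SD on a factor outside the rule. Unrestricted random splitting gives much the same for a factor unrelated to the scores: the SE is √(2/20) = 0.316 SD, 0.5/0.316 = 1.58, and the two-sided tail is 11.4%. So matching does almost nothing for such a factor. Under a random choice the 5% level allows for these imbalances; under a choice related to prognosis it does not.

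**3. What would a systematic choice do to the test?**
- Assumed: imbalance d of 0.2-0.5 SD on an unmatched factor, and correlation r of 0.2-0.5 between that factor and change.
- Bias = d × r, from 0.2 × 0.2 = 0.04 to 0.5 × 0.5 = 0.25 SD of change.
- Test: t test on change, 38 df, critical value 2.024, noncentrality = bias/0.316. This runs from 0.04/0.316 = 0.13 to 0.25/0.316 = 0.79.
- R² is the share of change variance explained by the matched scores. The 25% column takes their group means as exactly balanced and the test as unadjusted, as planned.

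| Bias (SD of change) | Error, R² = 0 | Error, R² = 25% |
|---|---|---|
| 0.04 | 5.2% | 2.6% |
| 0.10 | 6.1% | 3.4% |
| 0.15 | 7.5% | 4.6% |
| 0.20 | 9.5% | 6.4% |
| 0.25 | 12.0% | 8.7% |

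With d and r each in steps of 0.1, 13 of the 16 combinations stay below 8% at R² = 0. At R² = 25%, 12 of the 16 have a bias of 0.15 or less and so stay below 5%.

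**The case against.** Much of the opposing case stands. This is a 40-person pilot with a feasibility goal, and the documents never call the trial randomised, so nothing is contradicted. An unwritten random step may exist. Assignment already comes after both baseline sessions.

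Levels 2 and 3 are analysed pre/post by group, so a plain baseline difference on those outcomes is partly handled; only factors that predict a different amount of change matter. The error figures are modest, and the largest assumed bias, 0.25 SD, is below one standard error of the group difference (0.316 SD). If children enter one at a time, the count of 40-child splits does not describe the assigner's actual choices.

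Two replies remain. First, even with a tight limit on range, many splits qualify and nothing says how one is chosen. Second, the lower error at R² = 25% arises because an unadjusted test is conservative after balancing; the bias in the estimated group difference is still d × r.

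A reader might infer that the groups will be unbalanced in favour of gaze training, or that the efficacy results are invalid. The documents support neither: they give no direction and show no actual imbalance.

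**Conclusion.** The concern holds as an exposure, not as a demonstrated bias. The omission itself is certain from the text; its consequence is not. The between-group tests at Levels 2 and 3 are the most exposed. Level 1 is less so, because its own scores are matched and the remaining route is through factors unrelated to them. The within-group pre/post comparisons and the single-case comparisons do not depend on how the groups were formed.

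An error near 12% should not be read as the expected size: it needs both d and r at 0.5 and matched scores that explain none of the change. The values of d, r, R², the score correlations and the tolerances are all assumptions. The point should be fixed because efficacy is a stated aim and analysis cannot fully repair allocation afterwards; pilot status and the partial matching keep it short of a fatal flaw.

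**What to change.** Replace the rule in the Assessment/Orientation Phase with a concealed random step that keeps balance on the Level 1 means.

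- **Batch entry:** list the allocations that meet pre-set limits on each Level 1 mean and on mean age, and draw one at random. Add a loose range limit where the batch is large enough.
- **Single entry:** use minimisation with a random element (0.8, for example) on the Level 1 scores and age.
- **Replacements:** use the same procedure.
- **Concealment:** keep the next assignment from those who enrol and test, and keep assignment after the Session 2 baselines.
- **Analysis:** compare groups on change or post-score, adjusted for that outcome's own baseline, the other balancing scores and age.
- **If allocation has already been made without a random step:** report the group comparison as non-randomised and adjust for age and baseline scores. If a random step was used, write it down.

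The change needs protocol text and a short script, with no extra participants, visits or tests. Batching may mean some waiting.

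The real cost is looser balance. In simulation under the same score assumptions, with age taken as uniform from 9 to 26, the 95th percentile of the worst of five mean differences is 0.20-0.22 SD with batches of 10. It is 0.41-0.43 SD with 0.8 minimisation and 0.79-0.82 SD with simple randomisation. Deliberate matching of all 40 reaches about 0.05 SD. Range is largely given up: it can differ by about 2 SD on one score. Adjustment largely offsets the looser means. For a Level 1 outcome, five scores and age leave 40 − 2 − 6 = 32 df (critical t 2.037 against 2.024); a Level 2 or 3 outcome's own baseline takes one more.

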Spatial Attention Task (E-Task): This task is patterned after Posner's classic cued spatial attention tasks, but uses target discrimination rather than detection. The task display is a central fixation cross on a computer monitor flanked by boxes on the left and right. Trials begin with either an attention directing cue (one of the boxes brightened) or a null cue (no change or both boxes brightened). Following a short (100 ms) or long (800 ms)

delay, a target (letter "E" pointing up, down, left or right) is presented in either the cued (valid) or the opposite uncued (invalid) location. The subject moves a joystick lever to indicate target orientation (up, down, left, right). Results from a number of studies using this task demonstrate slowed disengagement and shifting of attention in ASD children and adults. A study that used this task to examine spatial attention development in typically functioning children and adults will provide estimates of typical behavior on this task.

Analysis: Measures to be used from this task are: attention disengagement index (difference between accuracy to cued and uncued targets); attention orienting index (difference between cued targets with short vs. long attention orienting delays)³. Analyses for pilot testing to assess improvement in attentional skills will test the disengagement and orienting indices to: 1) compare individual participants against control performance (using means and variability from age-matched typical controls at pre- and post-testing ⁸. Simple analyses will use a t-test or repeated measures ANOVA to examine attention differences in pre- and post- measures and group differences and interactions.

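### Participants aged 9 to 26 are assigned by matching attention and eye movement scores only, and no between-group analysis includes age, although the plan expects children to benefit more than adults

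*Combined protocol and SAP*

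**What the plan says.** The aims describe "2 groups of 20 ASD children/teens/young adults (aged 9-26" years), and Research Design and Methods calls the whole sample children: "We will recruit 40 male and female children with ASD (ages 9-26) to participate in the clinical trial".

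Under Assessment/Orientation Phase, baseline scores on the Spatial Attention and Eye Movement tasks are used to "assign children to one of two intervention groups so that the mean and range of those scores are equivalent between groups". Age is not mentioned there, no random element is described, and the text does not say whether the scores are standardised for age.

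Participation of Children says that interventions of this type "are likely to be more effective in children than adults" and adds: "The goal of this study is to test whether our portable eye-tracking system is easy and durable for children's use at home".

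The group analyses are t-tests, repeated measures ANOVAs and, at Level 1, a MANOVA. They appear in the task-level Analysis paragraphs and in the Statistical Plan for Levels 1 to 3. Their terms are time, group and the interaction of the two.

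Age enters in one place. The E-Task analysis compares each participant with typical performance, "using means and variability from age-matched typical controls at pre- and post-testing", and draws on a study of "spatial attention development in typically functioning children and adults". The Gap-Overlap section adopts the same analyses by reference, and Level 1 of the Statistical Plan refers back to them as single-case analyses.

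**The concern.** The plan treats age as relevant in two ways. It judges an individual's score against people of the same age, and it expects more benefit at younger ages. The group comparison takes account of neither.

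On a measure that changes with development, a mildly affected young child and a more affected adult can have the same score. Matching on scores therefore need not match the groups on age or on deficit relative to age. If gain depends on age, part of a gaze-versus-joystick difference in gain could reflect which group is younger. The driving simulation and the social outcomes are the most exposed, because they are not among the matched scores. They are balanced on age only to the extent that the Level 1 scores track age.

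A second issue concerns the stated home-use goal, which is about children. No result for participants under 18 is planned, so the findings on ease of use and compliance would come from a pooled sample that includes young adults.

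**Working it through.** **Plan's own figure.** The sample is 40, as 2 groups of 20. The documents give no alpha, power, effect size or SD, so this number cannot be reproduced. Everything below is illustration, and each assumption is marked.

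**Inputs.** From the documents: 20 per group; ages 9 to 26; five Level 1 outcome measures (Statistical Plan, Level 1). Assumed: ages uniform over 9 to 26; age-score correlation r; age-gain correlation ρ; two-sided alpha 0.05.

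**Step 1: age gap if scores are unrelated to age.**
- SD of age = 17/√12 = 4.91 years.
- SE of the difference in mean age = 4.91 × √(2/20) = 1.55 years.
- 95% range = ±1.96 × 1.55 = ±3.0 years. The chance of a gap above 2 years is about 20%.

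**Step 2: age gap after score matching.** For one closely matched score, SE = 4.91 × √(1 − r²) × √(2/20), which is 1.34 years at r = 0.5. For five scores, a simulation of 1,000 trials took the best of 200 splits of 40 on means and ranges. The scores were correlated with each other only through age.

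| r | SD of mean-age gap (years) | Chance of gap > 2 years |
|---|---|---|
| 0 | 1.56 | 20% |
| 0.3 | 1.26 | 11% |
| 0.5 | 1.05 | 5% |
| 0.7 | 0.79 | 1% |

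Score matching thus balances age in part when the scores depend on age, and not at all when they do not.

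**Step 3: effect on the group difference in gain.** Shift in SD of gain = ρ × gap / SD of age. For a 2-year gap:
- ρ = 0.2: 0.2 × 2/4.91 = 0.08
- ρ = 0.3: 0.3 × 2/4.91 = 0.12
- ρ = 0.5: 0.5 × 2/4.91 = 0.20

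For comparison, the difference detectable with 80% power at 20 per group is (1.960 + 0.842) × √(2/20) = 0.89 SD.

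The assumed age spread matters little here. With r = 0, a gap of one SE shifts the difference by ρ × √(2/20) = 0.316ρ whatever the age SD, which is 0.06, 0.09 and 0.16 SD for the three values of ρ.

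**Step 4: what adjustment gains.** Adjusting for age multiplies the residual SD of gain by √(1 − ρ²). For a true difference of 0.8 SD (assumed), normal-approximation power moves from 0.716 to 0.733, 0.756 or 0.832 for ρ = 0.2, 0.3 or 0.5.

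**Step 5: a result for under-18s only.** With uniform ages, 9/17 of the sample is under 18, about 10.6 per group. The detectable difference rises to 2.80 × √(2/10.6) = 1.22 SD. A formal test in this subset would be imprecise.

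**The case against.** Several points on the other side are sound.

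- **Age is not ignored altogether.** A reader might infer that no analysis uses it. The single-case comparison does, for the E-Task and by reference for Gap-Overlap, and it would show each participant's deficit relative to age on those tasks. It is not stated for the Anti-Saccade, simulation or social outcomes, and it does not enter assignment or any group test.
- **A stable age effect does not inflate the key error term.** A reader might suppose that ordinary age variation adds noise to the group-by-time test. With two time points that test is a t-test on change, and an age effect that is the same before and after training cancels. Only an age difference in gain enters, and the documents give no size for one.
- **Unadjusted scores are an inference.** The assignment rule says only that scores are used. No age-norming is stated, but none is ruled out.
- **A hidden severity gap cannot be quantified.** One could compute how far equal scores conceal unequal age-relative deficit. Once an age-score correlation is assumed and the scores are held equal, that figure follows by construction and is not evidence.
- **Chance gaps average zero.** If splits behave as random, the test already allows for them. Adjustment still removes the shift from the gap that actually occurs, and the plan describes no random element.
- **The age mix is unknown.** Recruitment runs through a children's hospital institute and an existing pool of children and teens, so adults may be fewer than uniform ages imply. Aim 1 also openly includes young adults, so the mixing of ages conflicts only with the child-centred home-use goal.

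What remains is that age is absent from the assignment rule and from every between-group model, while the plan itself expects younger participants to respond better.

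**Conclusion.** The point holds for the group comparison, and its size is modest. Under uniform ages the mean-age gap has an SD of about 1.6 years if scores are unrelated to age, and about 1.05 years if five matched scores each correlate 0.5 with age. If those scores also share variation unrelated to age, matching balances age less well, with 1.34 years as the single-score value. A 2-year gap moves the difference in gain by 0.08 to 0.20 SD, against about 0.89 SD detectable. The age distribution and both correlations are assumptions, because the documents supply none of them.

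A reader might go further and infer that the group comparison is invalid, or biased in a known direction. The documents do not support that: they give no age distribution by group and no size for the age effect. The change is worth making because the plan names age as relevant, the information is already in hand, and the remedy is cheap.

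**What to change.** 1. **Assessment/Orientation Phase.** Balance the groups on age band (under 18, 18 and over) together with the Level 1 scores. Matching on age-standardised scores is an alternative only if norms exist for every matched task. None are stated for Anti-Saccade, and coverage of the full 9 to 26 range is not stated for the other tasks.
2. **Statistical Plan, Levels 1 to 3.** Include age and its interaction with time in the group comparisons. In a pre-post comparison this is the same as using age as a covariate for change. It adjusts for an age-related gain common to both groups. It does not test whether the gaze-versus-joystick difference itself varies with age, which 40 participants could not settle.
3. **Home-use goal.** Report ease of use and compliance separately for participants under 18, as description only. Play time and the experience questionnaire are already collected for each participant (Intervention Phase and Final Evaluation Phase).

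The cost is one more balancing factor and one error degree of freedom in a pre-post comparison (38 to 37). No new data are needed. If assignment has already taken place, items 2 and 3 can still be adopted.

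### Children who stop playing are replaced and no analysis set is named, so compliance and training gain would rest mainly on those who kept playing

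*Combined protocol and SAP*

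**What the plan says.** All references are to the combined protocol and SAP.

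- **Replacement.** The Intervention Phase section states: "Children who withdraw (or whose participation is terminated for failure to play the games) from the study will be replaced". The non-completion paragraph after the exclusion criteria adds: "If individuals are unwilling or unable to complete in-lab testing, we will recruit new participants to complete those experiments". It expects "no more than 10-15% of the clinical participants will fail to complete all in-lab testing". It also has a rule for training: if more than two participants "fail to complete more than four weeks of training", the team tries to improve the user experience and recruits again.
- **Goal.** Under Participation of Children, the study is to test whether the eye-tracking system is easy and durable at home, and whether the games motivate "compliance for almost daily use over an extended period".
- **Data.** Under Intervention Phase, "we will receive daily summaries of the amount of time each child has played the games". If play falls short, "we will contact the family and follow-up with a home visit to assess the problem if necessary". There is an interim visit: "Participants will return to our lab at 4 weeks, for an abbreviated round of tests", covering Level 1 only. An experience questionnaire is given at the 8-week visit.
- **Analysis.** The Statistical Plan covers outcome Levels 1 to 3 by MANOVA and repeated measures ANOVA. It names no analysis set and no method for missing data. It plans no compliance summary or denominator. It does not say whether a child who has stopped playing attends the later visits.

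**The concern.** The replacement rule selects the sample on the behaviour under study. A child who will not play answers the home-use question in the negative, and that child is the one replaced. The questionnaire on ease of use comes at week 8, so its answers will come mainly from families who stayed.

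The same selection reaches efficacy. In their usual form the planned analyses drop a child without a post-training record. If children who stop gain less, the gain among those retained is larger than the gain among all assigned. The group contrast is exposed as well, because only Group 1 has to calibrate an eye tracker, so the reasons for stopping may differ between groups.

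Two analysts could include or leave out the replaced children, report different compliance and efficacy results, and both be following the plan.

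**Working it through.** **Inputs from the document.** Two groups of 20 give 2 × 20 = 40, which agrees with the recruitment figure. The play target is 30 minutes × 5 per week × 8 weeks = 1,200 minutes. There is no power calculation and no training-loss rate to reproduce.

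**Assumptions.** A share p of assigned children stops: 5%, 10% or 15%. Among retained children, 80% meet the play target. Children who stop gain a fraction k of the retained gain: 0 or 0.5. The correlation ρ between tendency to keep playing and outcome change is 0.3 to 0.7.

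**1. Compliance and training gain.** To obtain 40 finishers, 40/(1−p) children are assigned on average. A child who stops cannot meet the target over all eight weeks, so the full-period share among all assigned is 0.80 × (1−p). If retained children gain g, the all-assigned gain is g[(1−p) + pk], and the retained gain overstates it by the factor 1/[(1−p) + pk].

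| p | Assigned | Lost | Completion, all assigned | 80% among retained becomes | Overstatement, k = 0 | Overstatement, k = 0.5 |
|---|---|---|---|---|---|---|
| 5% | 42.1 | 2.1 | 95% | 76% | 1/0.95: 5% | 1/0.975: 3% |
| 10% | 44.4 | 4.4 | 90% | 72% | 1/0.90: 11% | 1/0.95: 5% |
| 15% | 47.1 | 7.1 | 85% | 68% | 1/0.85: 18% | 1/0.925: 8% |

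Counted only over the final 40, completion is 100% by construction. For eye-tracker ease of use the base is Group 1 alone, where 20/(1−p) − 20 gives 1.1, 2.2 and 3.5 children lost.

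**2. Group comparison when there is no true effect.** Suppose the fraction f of a group with the lowest tendency to keep playing stops. The mean change among those retained then shifts by ρλ(f) SD, with λ(f) = φ(z_f)/(1−f), where z_f is the f-quantile of the standard normal. This gives λ = 0, 0.109, 0.195 and 0.274 for f = 0, 5%, 10% and 15%. The bias is ρ₁λ(f₁) − ρ₂λ(f₂). The error rate is that of a two-sided 5% t-test with 20 finishers per group, by simulation.

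| Loss in the two groups | Bias (SD) | Error rate |
|---|---|---|
| 15% and 15%, same ρ | 0 | 5.0% |
| 15% and 10% | 0.079 × 0.3 to 0.7 = 0.02 to 0.06 | 5.1-5.5% |
| 15% and 5% | 0.166 × 0.3 to 0.7 = 0.05 to 0.12 | 5.3-6.8% |
| 15% and 0% | 0.274 × 0.3 to 0.7 = 0.08 to 0.19 | 5.7-9.3% |
| 15% and 15%, ρ = 0.7 and 0.3 | 0.274 × 0.4 = 0.11 | 6.4% |

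Equal loss is therefore harmless only if loss relates to outcome in the same way in both groups.

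**3. The rule on more than two failures.** The document gives no base for it. Over 40 children, P(X > 2) is 32%, 78% and 95% at p = 5%, 10% and 15% if every failure comes by week 4, and 8%, 32% and 59% if half come later (p/2). Over a base of 20, with every failure by week 4, it is 8%, 32% and 60%. Either way the rule prompts action and does not estimate compliance.

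**The case against.** The case against has real strength.

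- **Nothing says that data are thrown away.** This stands. A reader might infer that replaced children's records are deleted, but the text only says that people are added. Play is logged for each child, so an all-assigned denominator can still be built. The gap is that no such analysis is planned.
- **The sizes are assumed.** This also stands. A reader might apply the plan's 10-15% to training, but it is stated for in-lab testing. The 18% needs children who stop to gain nothing. The drop from 80% to 68% follows from counting anyone who stops as not meeting the full-period target, whatever the reason for stopping.
- **Bias between the groups is mostly small.** Agreed. A reader might conclude that the group contrast is invalid, but the documents do not support that. The largest figure needs 15% loss against none and a correlation of 0.7, and the early phone calls and home visits should reduce loss.
- **It is a pilot, and compliance is not among the numbered aims.** Correct, but the section on participation of children states it as the goal, and the undefined population also affects the efficacy aim.
- **Other planned analyses help.** Single-case comparisons with control norms do not need a complete group dataset, though they do need post-testing. The planned non-linear trends imply use of week 4 for Level 1, but nothing provides for keeping a child who has week 4 and not week 8. Levels 2 and 3 have no week-4 test.
- **An all-assigned analysis lacks the backing of randomisation here.** This stands. Groups are formed by matching baseline scores, randomisation is not stated, and no rule says how replacements preserve the matching.

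**Conclusion.** The concern holds as a weakness of design and analysis that should be fixed. The replacement rule, the complete-record analyses and the unnamed analysis set together make it likely, though the document does not state it, that results describe children who kept playing.

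Compliance and ease of use would then look better than among all children assigned. The training gain would be overstated by about 5-18% if 5-15% stop and gain nothing, or 3-8% if they gain half as much. The group comparison may be off by about 0.02-0.19 SD when loss is unequal, and by 0.11 SD at equal 15% loss with correlations of 0.7 and 0.3.

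All loss rates, gain fractions and correlations are assumptions. The compliance point does not depend on unequal loss between groups and carries most of the weight. The documents do not show that data are discarded or that the group contrast is seriously distorted.

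**What to change.** - Count added participants as additional, not as substitutes, and keep every assigned child in the assigned group.
- Report by group the numbers assigned, withdrawn, terminated and replaced.
- Report logged play by group over all assigned children: minutes per week and the share meeting 30 minutes on 5 days. Count a child who stops as not meeting the target from that point on. Report eye-tracker ease of use over all children assigned to Group 1.
- Analyse outcomes in all assigned children with a method that keeps all available visits, including week 4 for Level 1; a mixed model is one option. Keep the finisher analysis as a sensitivity analysis.
- Where feasible, invite children who stop playing to the 4- and 8-week assessments already planned. For Levels 2 and 3, week 8 is the only source of post-baseline data.

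**Cost.** The reporting and analysis items are wording and use logs and visits already planned. At an assumed 10-15% loss, about 4-7 children would be invited back, for at most 8-14 visits. Those who return need payment and testing, and at week 8 also the driving simulation and the live interaction with its video coding. Some records will be incomplete and the observed effect may be smaller. Because allocation is by score matching and not stated to be random, the change reduces selection from dropout without giving the protection of randomisation.
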